3.1. Study Rationale

Study I6T-MC-AMBE (AMBE) will assess the pharmacokinetics (PK), safety and tolerability of, and pain associated with, a 125-mg subcutaneous (SC) dose of LY3074828 solution formulation administered using an investigational manual 1-mL pre-filled syringe (PFS) or an investigational 1-mL autoinjector (AI). Both devices will be evaluated at 3 different injection sites (arm, thigh, and abdomen) in order to expand the options for administration in patient use. The study will provide data to bridge PFS administration of LY3074828, with the investigational AI device planned for use in subsequent studies and patient use.

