7. SAMPLE SIZE JUSTIFICATION

Approximately 66 subjects will be enrolled with a target of 60 subjects completing the study (10 completers per treatment).

Data from AMAL (2 x 1-mL doses of 125 mg LY3074828) and AMAE (2 x 1-mL PFS doses of 125 mg LY3074828) studies showed that the geometric coefficient of variation (CV) ranged from 55% to 40% for the PK measurements (ie, area under the concentration versus time curve [AUC] from time zero to infinity [AUC($0-\infty$)], AUC from time zero to time t , where t is the last sample with a measurable concentration [AUC($0-t_{last}$)], and maximum observed drug concentration [C_{max}]). Thus, the geometric coefficient of variation was assumed to be 55% when calculating precision.

A sample size of 60 subjects will provide a precision (ie, half-width of 90% of confidence interval [CI] with a coverage probability of 90%), in log scale, of approximately 0.48 for the geometric means ratio of reference versus test for AUC($0-\infty$), AUC($0-t_{last}$), and C_{max} . Equivalently, there is a 90% probability that the distance between the lower limit of the 90% CI and the point estimate of the geometric means ratio is not larger than 38%.

Subjects who are randomized but not administered treatment, or subjects (maximum of 2 subjects per dose regimen arm) that are administered treatment but do not have PK and anti-drug antibody (ADA) samples collected up to and including Day 57, may be replaced to ensure that approximately 10 subjects from each treatment arm may complete the study.

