9.3.2 Pharmacokinetic Statistical Methodology

The $AUC(0-\infty)$, $AUC(0-t_{last})$, and C_{max} will be log-transformed and analyzed using a linear fixed-effects model. The model will include device and injection site as fixed effects. The differences between the AI (Test) and PFS (Reference) will be back-transformed to present the ratios of geometric least squares means and the corresponding 90% CI.

Example SAS code:

```
proc mixed data=datain alpha=0.1;
  class device inj_site;
  model log_pk = device inj_site / ddfm=kr alpha=0.1;
  lsmeans device / pdiff cl alpha=0.1;
  ods output lsmeans=lsmeans;
  ods output diff=diffs;
run;
```

The t_{max} of LY3074828 between AI and PFS administrations will be analyzed using a Wilcoxon rank sum test. Estimates of the median difference, 90% CIs, and p-values from the Wilcoxon rank sum test will be calculated.

In addition, the following comparisons will also be made:

- AI versus PFS separately at each injection site (injection site will be removed from the model above)

- Arm versus abdomen and thigh versus abdomen separately for each device (device will be removed from the model above)

Additional PK analyses may be conducted if deemed appropriate.

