9.4.6 Injection-Site Pain

Intensity of pain data will be quantified using a 100-mm validated VAS. The data will be listed and summarized by treatment and time point. In addition, the scores will be categorized into mild (0- to 30-mm), moderate (31- to 70-mm), and severe (71- to 100-mm), and presented in frequency tables by treatment and timepoint. Furthermore, scatter plots of the 1 minute, 5 minute, and 15-minute VAS scores will be presented by treatment and time point.

A linear fixed-effects model will be used to analyze the 1- and 5-minute post-injection pain VAS scores separately. The model will include device and injection site as fixed effects. The least squares means and differences between the AI (Test) and PFS (Reference) will be presented along with the corresponding 90% CI for the difference.

If the assumptions of this model appear to be violated, a non-parametric method may be used.

The distribution of the data will be explored prior to analysis to determine whether data transformation is required. It is possible that the pain scores will be 0, so if the distribution of the data implies that a log-transformation is required then the score may be updated to $\log(VAS+1)$ to allow for the inclusion of the 0 values in the analysis. If the assumptions of this model appear violated, a non-parametric method may be used.

The above analyses will also be repeated for each injection site separately.

SAS code similar to Section 9.3.2 will be used for this model.

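### Does the SAP need a device-by-site contrast to show whether the AI/PFS effect differs between arm, thigh and abdomen?

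*SAP*

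**What the plan says.** SAP 9.3.2 fits each log-transformed PK parameter on device and injection site without a product term ("model log_pk = device inj_site / ddfm=kr alpha=0.1") and requests least-squares means for device only ("lsmeans device / pdiff cl alpha=0.1"). It then lists two further sets of comparisons. The first estimates the device effect in its own fit for every site: "AI versus PFS separately at each injection site (injection site will be removed from the model above". The second turns this round and compares the sites, with abdomen as the comparator, in a fit of its own for the syringe and another for the autoinjector: "Arm versus abdomen and thigh versus abdomen separately for each device (device will be removed from the model above".

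The section closes with an open provision: "Additional PK analyses may be conducted if deemed appropriate". SAP section 3 also allows supplementary analyses, to be identified in the study report.

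SAP 9.4.6 uses the same main-effects model for the 1- and 5-minute VAS scores and adds: "The above analyses will also be repeated for each injection site separately". Protocol 10.3.1.2.1 and 10.3.2.2 likewise specify main effects only.

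The primary objectives (Protocol section 4, SAP 4.1) are PK with each device, and pain with each device at three sites. Protocol 3.1 gives the reason for the sites: "Both devices will be evaluated at 3 different injection sites (arm, thigh, and abdomen) in order to expand the options". Neither document sets equivalence limits or a rule that depends on the device effect being the same at every site.

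**The concern.** A main-effects model assumes a common device effect at all sites. If the AI raised exposure 1.5-fold at one site and not at the other two, the pooled ratio would centre on 1.5^(1/3) = 1.14 and hide the site that matters. The by-site fits would show three ratios, but a reader would have to compare them by eye. That can mislead in two ways: chance alone spreads the three ratios, and overlap of separate intervals is a conservative guide to whether two effects differ. In a study meant to bridge the syringe to the autoinjector at three sites, an unnoticed site difference could be carried into later use.

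**Working it through.** **Inputs.** 10 completers in each of 6 arms and 90% intervals with 90% assurance on the half-width (SAP 7). The geometric CV "ranged from 55% to 40% for the PK measurements", and the SAP assumes 55%. Log-scale SD: s = sqrt(ln(1 + CV²)) = sqrt(ln 1.3025) = 0.5141 at 55%, and sqrt(ln 1.16) = 0.3853 at 40%.

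**1. The plan's own figure.** Half-width with assurance = t(0.95, df) × s × sqrt(v) × sqrt(χ²(0.90, df)/df).

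- AI versus PFS at one site (v = 2/10, df = 18): 1.734 × 0.5141 × 0.4472 = 0.399 typical; × 1.2016 = **0.479** with assurance. 1 − exp(−0.48) = 38%. Both stated figures reproduce.
- Pooled device ratio (v = 2/30, df = 56): 1.6725 × 0.5141 × 0.2582 = 0.222; × 1.1174 = 0.248. This does not match.

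So the stated precision is that of the by-site device comparison, although SAP 7 speaks only of 60 subjects.

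**2. Precision of a between-site contrast** (v = 4/10).

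| CV | Typical, df 54 | With assurance, df 54 | With assurance, site-specific variances (df about 36) |
|---|---|---|---|
| 55% | 0.544 (×1.72) | 0.609 (×1.84) | 0.6286 (×1.875) |
| 40% | 0.408 (×1.50) | 0.456 (×1.58) | 0.471 (×1.60) |

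**3. Does the contrast see more than the by-site intervals?** At CV 55%, two typical by-site intervals separate at 2 × 0.399 = 0.797 (2.22-fold), and the contrast excludes 1 at 0.544 (1.72-fold). The contrast's standard error is 0.5141 × sqrt(0.4) = 0.325. Non-overlap therefore corresponds to 0.797/0.325 = 2.45 standard errors, a two-sided error rate of about 2%, against 10% for a 90% contrast. Simulation with 10 per arm and a true 1.5-fold difference at one site gives these detection rates per affected pair:

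| CV | Non-overlap (2% error) | 90% contrast (10% error) | Contrast held to 2% error |
|---|---|---|---|
| 55% | 12.9% | 34% | 13.3% |
| 40% | 23.4% | 50% | 24.0% |

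At equal error rates the two are practically the same.

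**4. Chance findings.** With no site difference, the largest of the three observed site ratios exceeds the smallest by a median factor of 1.44 at CV 55% (90th percentile 1.95), and by 1.31 (1.65) at CV 40%. The planned by-site intervals already convey this noise: each runs a factor of exp(0.399) = 1.49 either way at CV 55%. Three unadjusted 90% contrasts would exclude 1 at least once in about 22% of such trials per parameter, against about 5% for any non-overlap. Three PK parameters and two VAS times would make 3 × 5 = 15 intervals, and Protocol 10.3 makes no multiplicity adjustment.

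**5. Availability.** The by-site fits use different subjects, so a contrast is the difference of two reported log ratios, with standard error sqrt(0.2299² + 0.2299²) = 0.325, the same as from a six-cell model. For PK, the within-device site comparisons lead to the same ratio of ratios.

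**The case for a change.** The strongest case for adding the contrast is that the SAP prints three by-site results beside a pooled one and so invites comparison without supplying a statistic for it. The open provision on further analyses permits a contrast but does not pre-specify one, and in SAP 9.3.2 it covers PK only. One extra model would cost a few lines of code. With site-specific variances it would leave every planned estimate unchanged, and an interval reaching a factor of 1.72 or more each way would show plainly how little the trial can say about consistency across sites.

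The factual part stands: no device-by-site term or contrast is named, and a pre-specified interval would be tidy. The claimed benefit does not stand. The higher detection rate is bought with a higher error rate, and nothing in either document tells a reader to judge by overlap. The addition would also feed the error it is meant to prevent, because about one trial in five with no site difference would show an apparent one on a given parameter. With a real 1.5-fold difference at CV 55%, a given affected contrast would still include 1 in about two thirds of trials, which could be misread as reassurance.

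**Conclusion.** The concern does not hold. The plan estimates what its objectives ask for: a device effect averaged over sites and a device effect at each site, the latter with the precision the SAP states (0.479 recomputed, 0.48 stated). The pooled ratio is never the only result, so a device effect confined to one site is not left to a diluted average of 1.14. No planned estimate is wrong and no stated decision would change. Printing the between-site contrast is a reporting preference. It adds no detection at an equal error rate (about 13% at CV 55% and 24% at CV 40% for a 1.5-fold difference).

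These figures assume 10 completers per arm, log-normal PK parameters with equal variance in all arms, and a geometric CV between 40% and 55%. The documents give no SD for VAS, so for pain the conclusion rests on the structure of the plan: SAP 9.4.6 repeats the analysis at each site, and no rule depends on a difference between sites.

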The primary parameters for analysis will be $AUC(0-\infty)$, $AUC(0-t_{last})$, and C_{max} for LY3074828. The secondary parameter for analysis will be the time to maximum observed drug concentration (t_{max}) of LY3074828. Other noncompartmental parameters, such as half-life associated with the terminal rate constant ($t_{1/2}$), apparent total body clearance of drug calculated after extra-vascular administration (CL/F), and apparent volume of distribution during the terminal phase after extra-vascular administration (V_z/F), may be reported.

10.3.2.2. *Pharmacokinetic Statistical Inference*

The $AUC(0-\infty)$, $AUC(0-t_{last})$, and C_{max} will be log-transformed and analyzed using a linear fixed-effects model. The model will include device and injection location as fixed effects. The dosing regimen differences between AI and PFS administrations will be back-transformed to present the ratios of geometric LS means and the corresponding 90% CI. Comparisons will be made between the 2 devices and then between the 3 injection locations.

The t_{max} of LY3074828 between AI and PFS administrations will be analyzed using a Wilcoxon rank sum test. Estimates of the median difference, 90% CIs, and p-values from the Wilcoxon rank sum test will be calculated.

Additional PK analyses may be conducted if deemed appropriate.

10.3.3. *Pharmacodynamic Analyses*

This section is not applicable for this study.

10.3.4. *Pharmacokinetic/Pharmacodynamic Analyses*

This section is not applicable for this study.

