5. STUDY DESIGN

Study I6T-MC-AMBE (AMBE) is a single-center, randomized, parallel-arm, open-label, Phase 1 single-dose study of LY3074828 solution formulation in healthy subjects. Pharmacokinetics,

safety and tolerability of, and pain associated with, 125-mg SC doses administered using a PFS or AI at 3 different injection sites will be evaluated.

Screening Period (≤ 28 days): Subjects will be evaluated for study eligibility ≤ 28 days prior to enrollment.

Residential Period (2 days): A total of approximately 66 subjects who fulfill the eligibility criteria will be randomized to 1 of 6 dosing regimen arms, with 11 subjects randomized to each arm to ensure completion of 10 subjects in each:

- Test 1: 1-mL AI injector containing 125 mg LY3074828 solution to be administered in the arm
- Test 2: 1-mL AI injector containing 125 mg LY3074828 solution to be administered in the thigh
- Test 3: 1-mL AI injector containing 125 mg LY3074828 solution to be administered in the abdomen
- Reference 1: 1-mL PFS containing 125 mg LY3074828 solution to be administered in the arm
- Reference 2: 1-mL PFS containing 125 mg LY3074828 solution to be administered in the thigh
- Reference 3: 1-mL PFS containing 125 mg LY3074828 solution to be administered in the abdomen

Subjects will report to the clinical research unit (CRU) on Day -1 and will remain at the CRU until the scheduled procedures have been completed on Day 2. Study drug will be administered by investigative site staff by SC injection per the randomization scheme in the morning of Day 1 after an overnight fast.

Safety and tolerability will be assessed by clinical laboratory tests, vital sign measurements, 12-lead electrocardiograms (ECGs), recording of AEs and product complaints (PCs), physical examinations/medical assessments, immunogenicity, and injection-site assessments. Pain assessments will be made using an injection-site pain visual analog scale (VAS).

Outpatient Follow-up Period (12 weeks): The follow-up period will include outpatient visits for a total of 12 weeks (Days 4, 8, 11, 15, 22, 29, 43, 57, 71, and 85) following dose administration on Day 1 to assess the PK, safety and tolerability of, and pain associated with LY3074828 PFS and AI administrations. Assessment of pain at the Follow-up visits does not include VAS score.

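### The pooled autoinjector v syringe comparison of tmax ignores injection site; stratifying by site is a minor but nearly free improvement.

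*SAP*

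**What the plan says.** SAP 9.3.2 specifies the pooled analysis of log AUC(0-∞), AUC(0-tlast) and Cmax as a linear model: "The model will include device and injection site as fixed effects". The pain model in SAP 9.4.6 has the same two factors.

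For tmax, the same section says that the difference between AI and PFS will be "analyzed using a Wilcoxon rank sum test". Protocol 10.3.2.2 adds the outputs: "Estimates of the median difference, 90% CIs, and p-values from the Wilcoxon rank sum test will be calculated". Neither document mentions stratification or adjustment for site in this test.

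SAP 9.3.2 then lists further comparisons: "AI versus PFS separately at each injection site (injection site will be removed from the model above") and "Arm versus abdomen and thigh versus abdomen separately for each device (device will be removed from the model above"). Both are worded as changes to the linear model. The SAP does not say whether they also apply to tmax.

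The design has six device-by-site arms, "with 11 subjects randomized to each arm to ensure completion of 10 subjects in each" (SAP 5). The planned pooled device comparison is therefore 30 v 30 completers, made up of 10 v 10 at each site. Protocol 10.3.2.1 names tmax as the secondary PK parameter.

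**The concern.** The pooled tmax test is the only pooled device comparison with a specified test that leaves site out. No reason is given.

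Because the arms are equal, each device has the same mix of arm, thigh and abdomen injections, and a site effect cannot bias a common device shift. It does inflate the spread against which that shift is judged. The Wilcoxon null variance treats all 60 values as exchangeable, whereas the AI-PFS contrast actually varies only through within-site differences. The test then rejects less often than its nominal 10%, and the 90% CI covers more than 90%.

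The study is meant to bridge the syringe to the autoinjector, and tmax bears on the rate of absorption. In that setting a non-significant p-value is easily read as similarity between devices, so lost power errs in the unhelpful direction.

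**Working it through.** **Inputs from the documents.** Six equal arms with 10 completers each (11 randomized); 90% CI, equivalent to a two-sided test at 0.10; the PK sampling schedule.

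**Inputs that are assumptions.** The spread of tmax and any site effect on it. Sites are placed at -s, 0 and +s, with s in within-arm SD units and running from 0 to 1.5. The device shift for power is 0.6 SD.

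**The plan's own figure.** The only stated precision is a log-scale half-width of 0.48, for AUC and Cmax. With CV 55%, SD = sqrt(ln(1 + 0.55²)) = 0.514. For 10 v 10 (18 df), the half-width met with 90% probability is 1.734 × 0.514 × sqrt(2/10) × sqrt(25.99/18) = 0.479, and 1 - exp(-0.479) = 38%. Both stated numbers are reproduced for a 10 v 10 comparison, but they say nothing about tmax. The documents give no operating figure for that test.

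**Approximate check by hand.** Take the normal-theory analogue of the pooled test. Sites at -s, 0, +s add a variance of 2s²/3 to a within-arm variance of 1. The test uses 1 + 2s²/3, but the contrast has only the within-arm part. Actual error is therefore about 2 × P(Z > 1.645 × sqrt(1 + 2s²/3)):
- s = 0.25: 1.645 × 1.021 = 1.679, error 9.3%
- s = 0.5: 1.645 × 1.080 = 1.777, error 7.6%
- s = 1.0: 1.645 × 1.291 = 2.124, error 3.4%

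**Simulation of the rank tests.** 20,000 trials per setting, 10 per arm, nominal 10%, tie-corrected. The stratified test is van Elteren with weights 1/(N+1). In the tied rows, tmax is log-normal (assumed median 4 days, log SD 0.6) and rounded to the scheduled times.

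| Data | s (SD) | Error, unstratified | Error, stratified | Power, unstratified | Power, stratified |
|---|---|---|---|---|---|
| Continuous | 0 | 0.097 | 0.101 | 0.724 | 0.718 |
| Continuous | 0.25 | 0.094 | 0.101 | 0.713 | 0.717 |
| Continuous | 0.5 | 0.071 | 0.100 | 0.677 | 0.718 |
| Continuous | 1.0 | 0.031 | 0.103 | 0.521 | 0.715 |
| Continuous | 1.5 | 0.006 | 0.101 | 0.315 | 0.712 |
| Tied | 0 | 0.105 | 0.104 | 0.676 | 0.672 |
| Tied | 0.25 | 0.094 | 0.099 | 0.668 | 0.677 |
| Tied | 0.5 | 0.077 | 0.100 | 0.637 | 0.678 |
| Tied | 1.0 | 0.037 | 0.099 | 0.499 | 0.676 |
| Tied | 1.5 | 0.011 | 0.103 | 0.312 | 0.678 |

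With 11 per arm the errors are nearly the same and power is a few points higher throughout. With no site effect, stratifying costs under one point of power.

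**Confidence interval.** Unstratified Hodges-Lehmann 90% CI, 3,000 trials per setting, continuous data. At s = 0, 0.25, 0.5 and 1.0, coverage is 0.897, 0.898, 0.922 and 0.972, and mean width is 0.88, 0.91, 0.96 and 1.17 SD. A site-adjusted linear-model interval stays at about 0.86 SD.

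**What the shifts mean for tmax.** Assume a log SD of 0.55. Adjacent-site shifts of 0.25, 0.5 and 0.75 log units are then 0.45, 0.91 and 1.36 SD. The ratio of tmax between the two extreme sites is exp(2 × shift) = 1.65, 2.7 and 4.5.

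**The case against.** The strongest reply is that little depends on this test and that it errs on the safe side. tmax is secondary and absent from the objectives and endpoints table. No margin or decision rule uses its p-value or CI. The interval over-covers, and the primary AUC and Cmax comparison already adjusts for site. All of this stands and keeps the point minor.

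The reply is also right that the size is unknown. The 55% CV belongs to AUC and Cmax. The large losses need adjacent sites about 1 SD apart, which is a roughly threefold tmax ratio between extreme sites at a log SD of 0.55, and nothing in the documents points to a difference of that size.

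A reader might infer four stronger things that the documents do not support:
- That the plan expects sites to differ in absorption. Site is a design factor in the models; neither document states an expected difference.
- That all other PK models adjust for site. Only the pooled AUC/Cmax model does. The by-site models drop the term because they use one site, and in the by-device models site is the factor compared.
- That randomization is stratified by site. Subjects are randomized to one of six arms, and the balance comes from the equal arm sizes.
- That the stated level is wrong in any case. With no site effect it is correct.

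It may also be said that the by-site comparisons already deal with site. If they cover tmax, they do so at 10 v 10 only and do not replace the pooled estimate. If they do not, no site-free tmax comparison is planned. The wording leaves this open.

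**Conclusion.** The point holds as a minor gain in efficiency and consistency. The pooled tmax comparison is unbiased for a common device shift, but it is conservative to the extent that sites differ in tmax. The loss is negligible at adjacent-site shifts of 0.25 SD or less. At 0.5 SD, error is about 7-8% against 10%, CI coverage about 92%, and the power loss about 3-4 points. Near 1 SD, error is about 3-4% and power about 0.52 against 0.72 (about 0.50 against 0.68 with tied times).

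These figures rest on an assumed ordered site effect, an additive device shift of 0.6 SD and the planned equal arms. The true tmax spread and site effect are not in the documents. The primary PK conclusions are unaffected.

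**What to change.** In SAP 9.3.2, replace the pooled tmax test with a Wilcoxon test stratified by injection site (van Elteren). Estimate the AI-PFS shift by Hodges-Lehmann from within-site differences only, and obtain its 90% CI by inverting the stratified test, so that estimate, interval and p-value agree. State whether the by-site AI v PFS comparisons also apply to tmax and, if so, by which test. Record the change in SAP section 11, since Protocol 10.3.2.2 names the plain test.

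The cost is a few lines of SAP text and a little extra programming, mainly for the stratified interval. No data collection or sample size changes.

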3. INTRODUCTION

This SAP has been developed after review of the Clinical Study Protocol (final version dated 17 December 2018).

This SAP describes the planned analysis of the safety, tolerability and pharmacokinetic (PK) data from this study. A detailed description of the planned TFLs to be presented in the clinical study report (CSR) is provided in the accompanying TFL shell document.

The intent of this document is to provide guidance for the statistical and PK analyses of data. In general, the analyses are based on information from the protocol, unless they have been modified by agreement between Eli Lilly and Company and Covance Early Clinical (EC) Biometrics. A limited amount of information concerning this study (e.g., objectives, study design) is given to help the reader's interpretation. This SAP must be signed off prior to first subject administration for this study. When the SAP and TFL shells are agreed upon and finalized, they will serve as the template for this study's CSR.

This SAP supersedes the statistical considerations identified in the protocol; where considerations are substantially different, they will be so identified. If additional analyses are required to supplement the planned analyses described in this SAP, they may be performed and will be identified in the CSR. Any substantial deviations from this SAP will be agreed upon between Eli Lilly and Company and Covance EC Biometrics and identified in the CSR. Any minor deviations from the TFLs may not be documented in the CSR.

This SAP is written with consideration of the recommendations outlined in the International Conference on Harmonisation (ICH) E9 Guideline entitled Guidance for Industry: Statistical Principles for Clinical Trials¹ and the ICH E3 Guideline entitled Guidance for Industry: Structure and Content of Clinical Study Reports².

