11. CHANGES FROM THE PROTOCOL SPECIFIED STATISTICAL ANALYSES

There were no changes from the protocol specified statistical analyses.

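### The SAP replaces the protocol's comparison of the three injection sites with 10-versus-10 contrasts inside each device and omits arm versus thigh, losing about a third of the precision with no change declared

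*SAP*

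**What the plan says.** **Protocol 10.3.2.2.** AUC(0-∞), AUC(0-t_last) and C_max are analysed on the log scale in one linear model: "The model will include device and injection location as fixed effects". The section then states: "Comparisons will be made between the 2 devices and then between the 3 injection locations". It names no reference location and no split by device.

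**SAP 9.3.2.** The same two-factor model is kept, but the only least squares means statement in the example code is "lsmeans device / pdiff cl alpha=0.1". Two further sets of comparisons follow. One is AI versus PFS at each site. The other is "Arm versus abdomen and thigh versus abdomen separately for each device (device will be removed from the model above").

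**SAP 3.** The rule on differences is: "This SAP supersedes the statistical considerations identified in the protocol; where considerations are substantially different, they will be so identified".

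**SAP 11.** The declaration is: "There were no changes from the protocol specified statistical analyses".

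**The concern.** Read in sequence, the protocol's two sentences describe a main-effect comparison for each factor of one model. For location that means three pairs, each using every subject at the two sites concerned, whichever device was used.

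The SAP does something else. It cuts the data into two device subsets, compares sites inside each, and does so for two of the three pairs. The location question is then answered by four separate ratios per PK parameter, each from 10 versus 10 subjects, and by none that combines the devices. Arm versus thigh is not among them.

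This matters because Protocol 3.1 and 5.4 give wider choice of administration site as the reason for studying three locations. The SAP governs where it differs from the protocol, so the protocol's location comparison would drop out of the planned output, and a reader of SAP 11 would not know it.

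**Working it through.** **Inputs**
- Completers (SAP 7): "Approximately 66 subjects will be enrolled with a target of 60 subjects completing the study (10 completers per treatment"). This gives 10 per arm, 20 per location, 30 per device and 60 in all.
- Variability (SAP 7): "Thus, the geometric coefficient of variation was assumed to be 55% when calculating precision". Log SD s = sqrt(ln(1 + 0.55²)) = 0.5141.
- 90% two-sided CI. The assurance (the plan's coverage probability) is 90%.

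**Formulas**
- Half-width for n versus n: h = t(0.95, df) × s × sqrt(2/n).
- Half-width with 90% assurance: h × sqrt(chi²(0.90, df)/df).

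**The plan's own figure.** SAP 7 and Protocol 10.1 state about 0.48 in log scale, or 38%, for reference versus test. With 10 versus 10 and 18 df:
- h = 1.7341 × 0.5141 × sqrt(2/10) = 0.399
- with assurance: 0.399 × 1.202 = 0.479
- 1 − exp(−0.479) = 38.1%

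So the stated figure is reproduced, and it is a 10-versus-10 figure. The other layouts do not give it: 30 versus 30 (56 df) gives 0.248 and 20 versus 20 (56 df) gives 0.304.

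**Location ratio from the device + location model.** 20 versus 20; df = 60 − 1 − 1 − 2 = 56:
- h = 1.6725 × 0.5141 × sqrt(2/20) = 0.272, that is −24%/+31%
- with assurance: 0.272 × 1.117 = 0.304; lower limit at most 26% below the estimate

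**Location ratio within one device, as in the SAP.** 10 versus 10; df = 30 − 3 = 27 if all three sites are fitted:
- h = 1.7033 × 0.5141 × sqrt(2/10) = 0.392, that is −32%/+48%
- with assurance: 0.392 × 1.167 = 0.457; lower limit at most 37% below the estimate

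The SAP does not say whether all three sites are fitted or only the two compared. If only two, df = 18 and the half-widths are 0.399 and 0.479, as above.

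**Comparison**

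| Scale | Pooled | Within device | Pooled interval narrower by |
|---|---|---|---|
| 90% CI, 27 df | 0.272 | 0.392 | 31% |
| 90% CI, 18 df | 0.272 | 0.399 | 32% |
| 90% assured, 27 df | 0.304 | 0.457 | 33% |
| 90% assured, 18 df | 0.304 | 0.479 | 37% |

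The standard errors alone are 0.1626 and 0.2299, a 29% difference, because doubling n halves the variance. The remainder comes from the degrees of freedom. At the lower CV of 40% (s = 0.3853) the half-widths are 0.204 and 0.294, and the relative loss is unchanged.

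**Contrasts planned, per PK parameter**

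| Pair | Across devices | Within each device |
|---|---|---|
| Arm / abdomen | not planned | planned |
| Thigh / abdomen | not planned | planned |
| Arm / thigh | not planned | not planned |

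**The case against.** **The protocol does not say the location comparison is pooled over devices, or that all pairs are meant.** True: that is the natural reading of a sentence that follows a two-factor model, not explicit text, and the synopsis mentions no location comparison. But even on a within-device reading, comparing three locations includes arm versus thigh, which the SAP omits.

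**The SAP adds rather than replaces.** Its extra comparisons are introduced as additional, its code is labelled as an example, and further PK analyses are allowed. None of this commits anyone to a location contrast from the main model. The additions supplement the device comparison, and permission for further analyses is not prespecification.

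**Arm/thigh can be recovered.** In part. Dividing the two within-device ratios gives the point estimate, and the `pdiff` option applied to site in a three-site model would print the pair. The interval does not follow from the two reported intervals alone, because both share the abdomen group. It also needs the residual variance and group sizes. What is missing is a commitment to report the ratio with its CI.

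**The SAP contrasts meet the planned precision.** This stands: 0.457 to 0.479 is within the stated 0.48. The point is precision left unused, not a shortfall against the sample-size statement.

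**Pooling assumes no device-by-location interaction.** It does, and the within-device contrasts avoid that assumption. The SAP already accepts it in its main device comparison. Keeping both sets of contrasts loses nothing.

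**The consequence is limited.** The primary PK objective names the devices, not the sites, and no margin or decision rule is set for a location ratio. The narrower interval would therefore change no prespecified conclusion, and the data are collected either way. This limits the weight of the point but does not remove the discrepancy.

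**Conclusion.** The concern holds. The SAP plans no location ratio across devices and no arm/thigh ratio, although the protocol calls for a comparison of the three locations, and SAP 11 declares no change. The within-device intervals are 1.44 times as wide as those the protocol's own model would give (1.50 times with 90% assurance, both at 27 df). Put the other way, the pooled interval is 31% to 37% narrower, depending on the degrees of freedom and on whether assurance is included.

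These figures assume 10 completers in each arm, equal variance across arms and no device-by-location interaction. The absolute half-widths use the planned CV of 55%; the relative loss does not depend on the CV. The primary device comparison is unaffected. This should be corrected, but it does not undermine the trial.

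**What to change.** In SAP 9.3.2:
- add `lsmeans inj_site / pdiff cl alpha=0.1;` to the main device + site model;
- report arm/abdomen, thigh/abdomen and arm/thigh as ratios of geometric least squares means with 90% CIs, labelled as the protocol's location comparison;
- keep the within-device contrasts as supportive, and state whether all three sites are fitted in each device subset.

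In SAP 11, record the within-device contrasts and any other difference from Protocol 10.3.2.2 that remains.

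The cost is one line of SAS code, one extra table block and a short text edit. No new data are needed.
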